| Visits, hospitalisations, exacerbations, sick leave, productivity | Previous year | | | | | | | |
| Allergy test = serum specific IgE test (pölyerittely) | x | | | | | | | |
| | x | | | | | | x | |
| ASA challenge test (to subjects without previous challenge-test-confirmed NERD dg) | | x | | | | | | |
| Treatment with IMP | | | x | x | x | x | | |
| Check side-effects | | x | x | x | x | x | x | x |
| ENT visit (+ lung examination) | x | x | x | x | x | x | x | x |
| Check CRS control | x | x | x | x | x | x | x | x |
| Pulmonologist visit | x | | | | | | x | |
| Check asthma control | x | x | x | x | x | x | x | x |
| Questionnaire-packet: SNOT-22, 15D, AQLQ, Asthma control | x | x | x | x | x | x | x | x |

| | | | | | | | | |
|---|---|----|---|---|---|---|---|-------------------|
| test, 2xNetherlands-Q | | | | | | | | |
| VAS symptoms | | x | | | | | | |
| Baseline characters questionnaire (esitietokaavake) | x | | | | | | | (x) if changed |
| Acoustic rhinometry (ARM) | x | xx | x | x | x | x | x | x |
| nNO | x | xx | | | | | x | |
| eNO | x | | | | | | x | |
| Olfaction Sniffin' sticks | x | | x | x | x | x | x | x |
| sinus CT scans | x | | | | | | | |
| Blood analysis for Biobank | x | | | - | - | - | | - |
| Blood samples (5 EDTA tubes) for metabolomics & genomics | x | xx | x | x | x | x | x | x |
| Urine samples for metabolomics | x | xx | x | x | x | x | x | x |
| Fecal sample for microbiome | x | | x | x | x | x | x | x |
| Nasal samples (microbiome, transcriptomics, histology) | x | xx | | | | | x | |
| Spirometry | x | | | | | | x | |
| PEF 1 week | x | x | | | | | x | |
| microspirometry | | x | | | | | | |
| PEF at visit | x | x | x | x | x | x | x | x |
| PNIF at visit | x | x | x | x | x | x | x | x |
| Check disease relapse | x | x | x | x | x | x | x | x |
| Consider additional therapy /referral to operation | x | x | x | x | x | x | x | x |

Study endpoints

Primary, Change from baseline

endoscopic nasal polyp score (total score ranges between 0-8 of both sides), SNOT22 symptom score, VAS score (of smell loss, obstruction, postnasal drip, nasal discharge, facial pain/pressure) and, exacerbation-rate. Exacerbation means that patient has at least one of the following due to airway symptoms: oral corticosteroid course; antibiotic courses; sinus lavation; hospitalization.

Secondary, Change from baseline

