No imputation methods were applied for missing data. To assess the robustness of the findings and the plausibility of the missing-at-random assumption, sensitivity analyses were performed. These included a complete-case analysis restricted to participants with available data at all time points and an analysis excluding participants who received systemic oral corticosteroids

for exacerbations at any point during the trial. The corticosteroid exclusion analysis evaluated the coprimary outcomes (Nasal Polyp Score and SNOT-22 total score) as well as lung function outcomes, including relative changes in peak nasal inspiratory flow, peak expiratory flow, forced expiratory volume in one second, and corresponding microspirometry measures. Sensitivity analyses were conducted in the per-protocol population on an available-case basis using the same statistical models, confidence intervals, and significance thresholds as the primary analyses. Consistency of results across analyses was used to support the validity of the primary findings. All statistical analyses were performed using R statistical software, version 4.5.1.

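### The two named sensitivity analyses cannot support the missing-at-random assumption or validate the primary result, and the corticosteroid exclusion is not a randomised comparison

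*SAP*

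**What the plan says.** The SAP's primary analysis fits random-intercept mixed models to the mITT set, relies on MAR and imputes nothing. On the checks it states: "To assess the robustness of the findings and the plausibility of the missing-at-random assumption, sensitivity analyses were performed". Two are named.

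- Complete cases: "These included a complete-case analysis restricted to participants with available data at all time points".
- Corticosteroid exclusion: "and an analysis excluding participants who received systemic oral corticosteroids" "for exacerbations at any point during the trial". It covers polyp score, SNOT-22 and the lung and nasal flow measures.

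On population and data basis: "Sensitivity analyses were conducted in the per-protocol population on an available-case basis", with the same models as the primary analysis. On use: "Consistency of results across analyses was used to support the validity of the primary findings".

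The protocol (section 2.1, Study endpoints) lists exacerbation rate among the primary endpoints and defines it: "Exacerbation means that patient has at least one of the following due to airway symptoms: oral corticosteroid course", followed by further components. The protocol Summary makes a reduction in exacerbations, measured partly by systemic corticosteroid use, an aim of the trial.

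**The concern.** Three features weaken the checks.

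1. The exclusion is defined by something that happens after randomisation and that the trial hypothesises treatment will change. If steroid use differs by arm and is related to the score, the participants left in each arm differ for reasons other than treatment.
2. MAR is an assumption about values nobody observed. Neither named analysis varies that assumption. One discards observed data and the other concerns rescue treatment.
3. Population and data handling change together, so a discrepancy with the primary result would have no identifiable cause.

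At stake is the SAP's robustness argument. A reader told that the results were consistent would take this as evidence about missing data that the analyses do not contain.

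**Working it through.** **Inputs.** From the protocol's power calculation: SD 17 and a SNOT-22 difference of 9. From the SAP: 47 per arm. Neither document gives corticosteroid rates, missing-data rates, or their correlation with outcome, so those below are assumptions. The power paragraph also prints a difference of 13. Only 9 reproduces its sample size: 2 × 17² × (1.960 + 0.842)² / 9² = 56.01, rounded up to 57 per arm, while 13 gives 26.8, or 27. I therefore use 9.

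**Step 1: corticosteroid exclusion.** Let the score be N(0, 17²) on placebo and N(-9, 17²) on mepolizumab, lower being better. A participant takes steroids when a latent propensity, correlated ρ with the score, exceeds a threshold c. With placebo rate p, c = z(1-p). With the same threshold in both arms, the effective threshold on mepolizumab is c' = c + ρ × 9/17. The mean among non-users is μ - 17ρλ(c), where λ(c) = φ(c)/Φ(c). Steroids are given no effect on the score, so this isolates selection.

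- p = 20%, ρ = 0.3: placebo 0 - 5.1 × 0.350 = -1.785; mepolizumab (c' = 1.000) -9 - 5.1 × 0.2874 = -10.466; difference -8.68.
- p = 40%, ρ = 0.7: placebo 0 - 11.9 × 0.6439 = -7.662; mepolizumab (c' = 0.624) -9 - 11.9 × 0.4476 = -14.326; difference -6.66.

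Estimated difference among non-users, true value -9:

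| Placebo steroid use | ρ = 0 | 0.3 | 0.5 | 0.7 |
|---|---|---|---|---|
| 20% | -9.00 | -8.68 | -8.15 | -7.40 |
| 30% | -9.00 | -8.61 | -7.94 | -6.99 |
| 40% | -9.00 | -8.55 | -7.78 | -6.66 |

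The attenuation runs from 0 to 2.34/9 = 26%.

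With no true effect on SNOT-22 but steroid use halved by the drug, the false difference (positive is against the drug) is 17ρ[λ(c for p) - λ(c for p/2)]:

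| Steroid use, placebo vs drug | ρ = 0 | 0.3 | 0.5 | 0.7 |
|---|---|---|---|---|
| 20% vs 10% | 0 | 0.79 | 1.32 | 1.84 |
| 30% vs 15% | 0 | 1.13 | 1.89 | 2.65 |
| 40% vs 20% | 0 | 1.50 | 2.50 | 3.50 |

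In this no-effect model, equal rates in the two arms also give zero.

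**Step 2: complete cases as evidence on MAR.** Take two follow-up visits correlated 0.5-0.7. The second is missing according to a latent variable correlated 0.6 with the unseen value itself, so MAR is false. The true benefit is 9. The MAR estimates come from simulation with 2 million per arm.

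- Missing 20% in both arms: complete-case and MAR estimates are both 9.0. They agree although MAR fails; each arm's complete-case mean is off by 17 × 0.6 × 0.350 = 3.6 points, and the errors cancel in the difference.
- Missing 20% vs 10%: complete-case gives 9 - 17 × 0.6 × (0.350 - 0.195) = 7.4. The MAR estimate is 7.8 to 8.1. Both are too small and err in the same direction. The gap of 0.3 to 0.7 between them would ordinarily be read as agreement, given a standard error of 17 × √(2/47) = 3.5 for the treatment difference.

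Conversely, Step 1 contains no missing data, yet the exclusion estimate departs from -9. A disagreement of that kind says nothing about MAR.

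**Step 3: population and wording.** The primary analysis is mITT; the sensitivity analyses are per-protocol, a set not defined in the text available. Requiring data at every time point and using whatever data are available are opposite rules, yet the SAP's sentences, read together, apply both to the complete-case run.

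**The case against.** The strongest reply is that these are only sensitivity analyses. Nothing in the SAP removes steroid users, or their later values, from the mITT primary analysis, so its estimate, interval and p-value do not change. This stands.

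The SAP also gives two purposes, robustness and MAR. The exclusion covers lung and nasal flow as well as the coprimary endpoints, which reads as a check on steroid influence over the measurements. A reader might infer that the SAP offers the exclusion purely as a test of MAR; the text does not say so. Wanting to examine steroid influence is legitimate, but the selection problem applies under either purpose.

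A reader might also infer that the exclusion certainly drops the worst responders, mostly from placebo. No data in the documents show this. The bias vanishes if steroid use is unrelated to outcome. In every scenario above where bias arises it runs against the drug, so no mechanism for manufacturing benefit has been shown.

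The phrase about available cases may have been meant only for the exclusion analysis. That is possible, but the sentence refers to the sensitivity analyses generally.

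Finally, the SAP's list is introduced as non-exhaustive and part of the SAP was not available for this review. A further sensitivity analysis or a per-protocol definition may exist, so the point is limited to the analyses named.

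**Conclusion.** The point holds in limited form and should be fixed; the sensitivity section is wrong as written. Agreement of the two named analyses with the primary result is not evidence that MAR is plausible, and the corticosteroid-exclusion comparison is not randomised. The change of population and the conflicting case-basis wording make any discrepancy uninterpretable.

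The size of the exclusion bias is illustrative only: 0 to about 2.3 points on a true 9, or a false difference of 0 to 3.5 points when there is no effect. It depends on the assumed steroid rates and correlations, and on a model in which steroids do not alter the score.

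A reader might go further and conclude that the primary result is invalid or biased. The documents do not support that. What falls is the validation claim built on these analyses.

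**What to change.** 1. Replace the complete-case check with a delta-adjusted (tipping-point) multiple imputation of missing polyp score and SNOT-22 at the follow-up visits, in the mITT set with the primary model. Describe it as showing how far MAR must fail before the conclusion changes; it does not test MAR either.
2. Stop using the corticosteroid-exclusion analysis to validate the primary result. If it is reported, label it exploratory and non-randomised. Any analysis of corticosteroid use offered as support should keep all mITT participants and state its estimand. The choice of estimand is the trial team's to justify.
3. Reconcile the complete-case and available-case wording, and run the sensitivity analyses in the mITT set so that one thing changes at a time.

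The cost is revised SAP text and slightly more analysis work on data already held. The SAP describes the analyses largely in the past tense and reports the code as opened after the primary analyses, so anything added after unblinding must be labelled post hoc.

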Other medication such as dosing-up medication, and medication of exacerbations (antibiotics, bronchodilators, nasal decongestants, systemic corticosteroids)

BEos, NPeos

signs of Type2-inflammation in blood and nasal samples

nasal and lung function test results (FEV1, peak expiratory flow rate, eNO, nNO and/or MCA in Acoustic rhinometry, PNIF, Sniffin' sticks 12)

Number of patients who met criteria for requiring surgery for polyposis at each time point

Questionnaire-packet: 15D, mini-AQLQ, Asthma control test, iMCQ, iPCQ, WPAI, EQ-5D-5L

Consideration/planning of a CRS-operation due to airway symptoms

Cost-effect and productivity (iMCQ,iPCQ questionnaires, sick leaves due to airway symptoms)

Safety (adverse effects)

The following clinical data are also collected:

Lund-Mackay score of Sinus CT scans/Cone beam CT, performed ~~12 months~~ prior to the study.

Questions concerning uncontrolled CRS according to EPOS12 and EPOS20 -criteria

The patient will know the treatment arm when the trial has been terminated. The patient can discuss with the doctor of the need to continue or start with advanced or another therapy or referral to consideration of operation, if needed. Results of the samples will be compared with the results of other studies (AirGOs-oper and AirGOs-medical).

Reporting and monitoring of adverse events and -reactions

Reporting of adverse events and -reactions is performed as follows: immediate announcement to the healthcare personnel, the patient and the principal investigator, and by recording and transferring the data to an electronic follow-up form (eCRF). The report will be forwarded to the supervisory authorities if necessary.

The subject's condition is monitored and treatment is carried out properly. eg. (medical care, treatment calls, medical appointments, if necessary), and all contacts between the study patient and the study unit are recorded in the patient records and eCRF-form and the necessary reports are submitted to the supervisory authorities if necessary.

Pharmaceutical manufacturer GlaxoSmithKleine will also receive a safety report from the research unit on the incident.

Adverse event and reaction reporting-, monitoring and registration is performed in accordance with Finnish legislation. We follow EU-standards and guidelines as well as the Declaration of Helsinki of the World Medical Assembly.

Pregnancy:

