The statistical analyses will be conducted in the modified intention-to-treat (mITT) population, defined as all randomized participants who received at least one dose of the investigational medicinal product and fulfilled the inclusion criteria. One randomized participant was excluded due to failure to meet inclusion criteria, resulting in 47 participants per treatment group. All analyses were performed blinded to treatment allocation, and the randomization code was opened only after the trial was closed and the primary analyses completed. The sample size was calculated to provide 80% power to detect clinically meaningful differences in the coprimary endpoints using a two-sided significance level of 0.05. Baseline was defined as the recruitment visit, occurring approximately eight weeks prior to initiation of the investigational medicinal product. Participants received four injections over a 16-week treatment period, followed by an additional eight-week observation period without treatment, after which final measurements were obtained. Continuous variables are summarized using means with standard deviations or medians with interquartile ranges, as appropriate, and categorical variables using frequencies and percentages. The coprimary endpoints and all secondary continuous outcomes were analyzed as changes from baseline using linear mixed-effects models. These models included fixed effects for treatment group, time, and their interaction, and a random intercept for participants to account for within-subject correlation over repeated measurements. Group-specific changes from baseline were estimated at each follow-up time point, and treatment effects were assessed by comparing differences in these estimated changes between groups. Results are reported as mean differences with 95% confidence intervals. A two-sided significance level of $p < 0.05$ was applied to all analyses, and no formal adjustment for multiple comparisons was performed. Model assumptions were evaluated by visual inspection of residual plots to assess normality and homoscedasticity, and by examination of fitted values and influence diagnostics to identify outliers or model instability. The linear mixed-effects modeling framework was selected because it accommodates unequally spaced measurements and missing observations and provides unbiased estimates under the missing-at-random assumption.

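### Relative change is named for PNIF, PEF, FEV1 and microspirometry only in the corticosteroid-exclusion analysis; the main-analysis scale is not stated, so disagreement between the two could come from scale alone

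*SAP*

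**What the plan says.** The SAP's main statistical paragraph sets the general rule: "The coprimary endpoints and all secondary continuous outcomes were analyzed as changes from baseline using linear mixed-effects models". It adds: "Results are reported as mean differences with 95% confidence intervals". Neither sentence says whether the change is in measured units or relative to baseline.

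The Protocol (2.1 General, Study endpoints) lists these tests as secondary, under a heading that says only that they are changes from baseline: "nasal and lung function test results (FEV1, peak expiratory flow rate, eNO, nNO and/or MCA in Acoustic rhinometry, PNIF, Sniffin' sticks 12". No relative scale is named there either.

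The SAP's paragraph on missing data and sensitivity analyses describes the analysis that excludes participants given systemic oral corticosteroids. Besides NPS and SNOT-22 it covers tests of airway function, described as "including relative changes in peak nasal inspiratory flow, peak expiratory flow, forced expiratory volume in one second". The matching microspirometry readings are listed too. No formula for relative change is given. On the analysis set, the same paragraph states: "Sensitivity analyses were conducted in the per-protocol population on an available-case basis". On method, it says that these analyses were run "using the same statistical models, confidence intervals, and significance thresholds as the primary analyses". On interpretation, it says: "Consistency of results across analyses was used to support the validity of the primary findings".

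**The concern.** A sensitivity analysis is informative when it changes one thing and keeps the rest. Here the comparison with the main analysis is used as evidence, but the outcome scale is either different or unstated.

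If the main analysis uses measured units, the mean differences for PNIF, PEF and FEV1 are in flow or volume units in one analysis and in per cent in the other. Their sizes and intervals cannot be compared directly. A result that gains or loses significance could be credited to steroid courses when the scale produced it.

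If the main analysis is also relative, the SAP and Protocol do not say so, and the scale of several secondary endpoints stays open.

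The relative scale also has a weakness of its own. Dividing by a small, noisy baseline makes the error grow as the baseline falls, which works against the constant-variance assumption of the linear mixed model. PNIF is the likeliest place for this, because entry requires a bilateral polyp score of at least 5 of 8 and no minimum PNIF is set.

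**Working it through.** **Plan's own figure.** There is none for these outcomes. The only sample-size calculation in the Protocol is for SNOT-22. It reproduces at 57 per arm with a difference of 9 and SD 17, and has no bearing on this point.

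**Inputs from the documents.** 47 per arm; two-sided 0.05 (SAP). No mean, SD, correlation or distribution is given for PNIF, PEF or FEV1, so everything below is conditional on assumed values.

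**Why low baselines matter (illustration).** Take an unchanged patient whose baseline is misread by 10 units.
- True value 100: the apparent change is 100/90 − 1 = +11% or 100/110 − 1 = −9%.
- True value 20: the apparent change is 20/10 − 1 = +100% or 20/30 − 1 = −33%.

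The same error gives a wider and more skewed result at the low baseline.

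**Simulation.** One follow-up visit, baseline B and follow-up Y, 4,000 trials per setting, nobody excluded and no steroid effect. Each trial was tested four ways: t-test on Y − B; t-test on 100(Y − B)/B; t-test on log(Y/B); and ANCOVA of Y on arm and B.

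Assumed mean, coefficient of variation (CV), correlation (r), effect as a share of the mean, and floor:
- FEV1-like: 2.8, 0.28, 0.85, 9%, 0.5
- PEF-like: 430, 0.25, 0.80, 9%, 60
- PNIF-like: 110, 0.45, 0.60, 24%, 20
- PNIF-like, low baselines: 90, 0.50, 0.50, 29%, 10

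The last column is the share of trials in which absolute and percent change disagreed on p<0.05.

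| Setting | Absolute | Percent | Log ratio | ANCOVA | Disagree |
|---|---|---|---|---|---|
| FEV1, normal, additive | 81% | 70% | 74% | 83% | 13% |
| PEF, normal, additive | 78% | 68% | 72% | 81% | 12% |
| PNIF, normal, additive | 82% | 52% | 71% | 88% | 31% |
| PNIF low, normal, additive | 79% | 34% | 65% | 90% | 47% |
| FEV1, log-normal, proportional | 77% | 78% | 79% | 79% | 8% |
| PEF, log-normal, proportional | 75% | 75% | 76% | 78% | 6% |
| PNIF, log-normal, proportional | 74% | 74% | 77% | 80% | 12% |
| PNIF low, log-normal, proportional | 71% | 68% | 74% | 79% | 14% |

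The estimated direction differed between absolute and percent change in 0.2–7% of trials.

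**Crossing distribution with effect type.** In a wider set of 20 scenarios, with additive and proportional effects under both distributions:
- Normal data: power 76–80% for absolute change and 31–71% for percent change; disagreement 11–47%.
- Log-normal data: power 72–81% and 70–88%; disagreement 6–16%.

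The distribution therefore matters more than the effect type. With log-normal data and an additive effect (CV 0.45, r 0.7), percent change had more power than absolute change, 88% against 79%.

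**Check on ANCOVA.** I repeated a 20-scenario grid with the effect set at 2.8 × SD(change) × √(2/47). Raw-value ANCOVA beat absolute change throughout. It beat percent change in all but two scenarios, both log-normal with an additive effect, where it trailed by about 2 points (81% against 83%; 83% against 85%). Disagreement with normal data reached 49–51% in the low-baseline setting, so the upper end of that range depends on how low baselines are allowed to go.

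**The case against.** The strongest objection is that the mismatch is inferred. A percent change is a change from baseline, the difference between arms in percent change is a mean difference, and the SAP says the sensitivity analyses used the same statistical models. All of this fits a relative outcome in both analyses. That stands. A reader might infer that the main analysis is absolute and that the SAP contradicts itself; the documents do not say so. What remains is that the scale is unstated in one place and named without a formula in the other. The same-models clause covers models, intervals and thresholds, not the definition of the outcome.

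A reader might also infer that relative change always loses power. It does not: with log-normal data the loss against absolute change is about nil, and it can become a gain.

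Nor does a positive mean percent change in an unchanged group bias the comparison. It affects both arms alike, and the type I error of percent change in null simulations was 4.1–4.9%.

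It would be too strong to say that the two analyses cannot be compared, because direction almost always agrees. It would also be too strong to say that percent change fails at low baselines. The documents report no PNIF values, the simulations used floors of 10 or 20 for PNIF and so never tested zero, and the SAP provides for residual plots and influence diagnostics. Those checks could reveal instability, but they do not settle which scale was meant.

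Finally, the sensitivity analysis also moves from mITT to per-protocol, so a discordant result would be ambiguous even on one scale. That is true, and it is a reason not to add a further, avoidable cause.

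**Conclusion.** The point holds as a gap in specification with a likely, unproven mismatch. The SAP should not treat agreement for PNIF, PEF, FEV1 and microspirometry as support until the scale is stated and shared.

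If the scales do differ, scale alone would produce disagreement on p<0.05 in about 6–16% of trials with log-normal data and 11–47% with normal data, at roughly 70–80% power for absolute change. These figures rest on assumed CVs of about 0.25–0.50, correlations of about 0.5–0.85 and a single follow-up visit, not on trial data. The consequence is greatest for PNIF.

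The scope is limited to secondary lung and nasal function outcomes and one sensitivity analysis. NPS and SNOT-22 are not touched.

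**What to change.** State one scale for PNIF, PEF, FEV1 and microspirometry and use it in both the main and the corticosteroid-exclusion analyses. The preferred form is the measured value, or its log where no zeros occur, with treatment, visit, their interaction and the baseline value as covariate. If a percentage is wanted, give its formula and show it descriptively, without testing it.

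The change has to be made in both SAP paragraphs. Deleting the reference to relative changes from the sensitivity paragraph alone would create a mismatch if the main analysis is in fact relative.

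With baseline as a linear covariate, modelling Y or Y − B gives the same treatment effect (Y − B = a + bB + cG is the same as Y = a + (b + 1)B + cG), so an absolute-change model needs only the added covariate.

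Two details need attention. Protocol Table 1 schedules spirometry at recruitment and week 16 only, so for spirometric FEV1 the model reduces to ANCOVA at one visit. Table 1 shows microspirometry only at the ASA-challenge visit, so its baseline and follow-up visits should be named.

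The cost is a short SAP edit in two places, a rerun of existing code, and the loss of per-patient percent change as a tested outcome. The fix removes scale as an explanation for disagreement; it does not separate the steroid exclusion from the move to per-protocol.
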